5.4 Treatment Discontinuation and Withdrawal of Subjects

5.4.1 Discontinuation from Study Treatment

Subjects who permanently discontinue study treatment will attend a safety follow-up visit at 30 ± 7 days after the last dose of guadecitabine or prior to the start of alternative anticancer therapy, whichever comes first. Reasons for treatment discontinuation could include the following:

- Investigators can discontinue subjects from study treatment in case of unacceptable toxicity, noncompliance, disease progression requiring alternative therapy, or if the investigator determines it is in the subject's best interest.
- Astex Pharmaceuticals may require that a subject is discontinued from treatment for safety reasons or for noncompliance.

In all cases, the reason(s) for discontinuation from study treatment must be recorded in the source document and on the relevant page of the subject's case report form or electronic case report form (CRF/eCRF).

5.4.2 Withdrawal from the Study

Subjects may withdraw consent for the study at any time, or subjects may be lost to follow-up. It is important to obtain follow-up information, according to standard medical practice, on any subject withdrawn prematurely from the study. Every effort must be made to undertake at least standard assessments that are critical for safety evaluation, such as adverse events.

Astex Pharmaceuticals may stop the study at any time. In this event, Astex will make reasonable efforts to ensure subjects are transitioned off study in an orderly manner.

6.0 ENROLLMENT PROCEDURES

Subjects will be screened at each study center for assessment of eligibility for the study. This screening may start once the date of data cut-off for the prior study has been determined.

All screened subjects will be assigned a unique identifier that will include the study number from their prior study.

7.0 STUDY TREATMENTS

Guadecitabine is the Investigational Medicinal Product (IMP).

7.1 Investigational Medicinal Product (IMP): Guadecitabine

Guadecitabine (2'-deoxy-5-azacytidylyl-(3' \rightarrow 5')-2'-deoxyguanosine sodium salt is a dinucleotide incorporating decitabine with deoxyguanosine via a $3'\rightarrow$ 5' phosphodiester bond.

7.1.1 IMP Information

Guadecitabine (SGI-110) will be supplied in a two-vial configuration.

SGI-110 for Injection, 100 mg is a glass vial containing lyophilized guadecitabine drug powder for reconstitution and SC injection using the custom diluent supplied in a separate vial. Each vial is stoppered and sealed with a flip-off cap.

SGI-110 Diluent for Reconstitution, is a glass vial of custom diluent. Each vial is stoppered and sealed with a flip-off cap. The diluent comprises 3 commonly used excipients, propylene glycol, glycerin, and ethanol, which are generally recognized as safe.

The sponsor recommends following Occupational Safety and Health Administration (OSHA) Guidelines for handling cytotoxic drugs outlined in Yodaiken and Bennett (1986) or similar institutional or country-specific guidelines. Preparation should occur according to institutional practice. For skin contact or spillage, refer to the material safety data sheet (MSDS) for treatment options.

Reconstituted drug product is intended for SC administration at a recommended concentration of 100 mg/mL.

Records of the receipt and dispensing of drug supplies will be kept at the study centers and reconciled at the end of the study to provide a complete accounting of all used and unused IMP.

Please refer to the SGI-110-12 Pharmacy Manual for further information on guadecitabine including storage conditions.

7.1.2 IMP Regimens and Administration

Subjects will receive guadecitabine treatment at the same dose that they were receiving in the last cycle of their prior study or at a different dose as guided by the dose adjustment guidelines in the prior study protocol. Subsequent treatment delays and/or dose reduction are at the discretion of the investigator as guided by the dose adjustment guidelines of the prior study protocol. Treatment may continue as long as the subject continues to benefit based on investigator judgment.

Administer guadecitabine by SC injection, preferably in the abdominal area, upper thigh, or arm. The total amount (in mg) of guadecitabine to be administered is determined by body surface area (BSA). In calculating BSA, use actual heights and weights. Do not adjust to "ideal" body weight. The institutional standard for calculating BSA is acceptable.

Take care to avoid intradermal injection, as this may result in injection site pain (see Section 8.4).

Additional guidelines regarding SC injection will be detailed in the SGI-110-12 Pharmacy Manual.

Investigators are prohibited from supplying guadecitabine to any subject not enrolled in this study or to any physicians or scientists except those designated as sub-investigators. The investigator must ensure that subjects receive guadecitabine only from personnel who fully understand the procedures for administering the study treatment.

There is no restriction on the use of best supportive care or hydroxyurea. Subjects who need to receive other anticancer therapies or other investigational treatments will be withdrawn from this study.

7.2 Guidelines for Adjusting or Withholding Study Treatment

Treatment delays and/or dose reduction are at the discretion of the investigator as guided by the dose adjustment guidelines of the prior study protocol.

7.3 Concomitant Treatment

On the concomitant medication eCRF, document all medications a subject takes, starting from the first day of treatment in this study and ending 30 days after the last dose of study treatment or when the subject begins alternative anticancer therapy, whichever comes first. Include supportive or palliative treatment (see Section 7.3.1) whether prescription or nonprescription, and medications taken for procedures (eg, biopsy). Include start and stop dates and indication. Preventive measures may be prescribed according to institutional and standard practice.

7.3.1 Supportive, Prophylactic, or Other Treatments

There is no restriction on the use of best supportive care or hydroxyurea. Give supportive treatment according to the institutional standard practice or other established standard of care guidelines.

7.3.2 Prohibited Medications

Other anticancer therapies (except those specified in Section 7.3.1 above) are not to be used. Cytotoxic chemotherapy and investigational treatments are prohibited for as long as subjects remain on study treatment.

Vaccination with live vaccines is prohibited while subjects remain on study treatment.

Subjects who need to receive other anticancer therapies or other investigational treatments will be withdrawn from this study.

7.4 Overdose Instructions

Record the actual dose of study drug administered in the source document and on the Dosing CRF/eCRF. Record any adverse clinical signs and symptoms associated with a potential overdose on the adverse event (AE) CRF/eCRF. Report signs and symptoms of a potential overdose that meet SAE criteria (defined in Section 10.1.2) to Astex on the SAE form within 24 hours (see

Section 10.3). Treat any AE (including SAE) based on standard care for the specific signs and symptoms.

8.0 RISKS/PRECAUTIONS

Refer to the Guadecitabine IB for the most current risks and precautions, as well as a complete list of AEs considered expected with guadecitabine therapy.

Since guadecitabine is an investigational drug, unexpected and potentially clinically significant AEs or SAEs may occur with its use. All subjects treated with guadecitabine should be closely monitored. The active metabolite of guadecitabine is decitabine so all events expected with decitabine (as described in Dacogen package insert [US] and Dacogen summary of product characteristics [EU]) would also be considered expected for guadecitabine.

Guadecitabine should not be given to women who are pregnant or to subjects with known sensitivity to decitabine.

8.1 Dose Limiting Toxicities

Dose limiting toxicities related to myelosuppression occurred in 2 subjects with MDS in the Phase 1 Dose Escalation (SGI-110-01) for the 5-day regimen at a dose of 125 mg/m² SC and included thrombocytopenia (Grade 4), neutropenia (Grade 4), and sepsis (Grade 5).

8.2 Myelosuppression (Neutropenia, Febrile Neutropenia, Thrombocytopenia, and Anemia) and its Consequences (Infections and/or Hemorrhage)

Myelosuppression and its consequences (pneumonia, sepsis, and other infections and/or hemorrhage from thrombocytopenia) are the primary toxicities associated with administration of guadecitabine and its effects after 5 consecutive days of administration are maximal between Days 15 and 22 in a cycle with recovery in 1 to 3 weeks. Pancytopenia is a hallmark of AML and MDS and may aggravate or obscure the effects of guadecitabine. However, if a clinical response occurs and normal hematopoietic cells repopulate the bone marrow, neutropenia and thrombocytopenia may abate.

Complete blood and platelet counts should be performed as needed to monitor counts. Since myelosuppression and infection events are also manifestations of the underlying disease of AML, MDS, and CMML, careful investigator judgment regarding relationship to treatment is important to guide the decision whether to dose delay, dose reduce, or both. The cyclic nature of myelosuppression (reduction of counts between Day 8-15 and trend to recover by Day 22-28 or later) could be more indicative of a drug effect, while persistent low counts regardless of treatment is probably more indicative of a disease effect that needs to be treated without dose delay. Investigators should use their clinical judgment guided by the recommendations for dose adjustment for guadecitabine in the prior study protocol.

8.3 Fertility

Decitabine, the active metabolite of guadecitabine, alters fertility and is mutagenic. Because of the possibility of infertility, men should have sought advice on cryopreservation of sperm, and women of childbearing potential should have sought consultation regarding oocyte cryopreservation before study treatment was started in the prior study. Women of child-bearing potential must not be pregnant or breastfeeding and must have a negative pregnancy test at screening. Women of child-bearing potential and men with female partners of child-bearing potential must agree to practice 2 highly effective contraceptive measures of birth control and must agree not to become pregnant or father a child while receiving treatment with guadecitabine and for at least 3 months after completing treatment.

8.4 Injection Site Reactions

Injection site reactions, such as pain, irritation, inflammation, erythema, and burning have been reported in the AML/MDS population and in subjects with solid tumors. Injection site reactions are related to guadecitabine SC administration and are mostly Grade 1 or 2.

Care must be taken to avoid intradermal injection. If injection site pain is reported, it could be avoided or diminished by slow SC injection and the application of ice packs to the injection site both before and after injection. If injection site pain is still clinically significant at subsequent injections despite slow injection and use of ice packs, pretreatment with topical or systemic analgesics can be considered. In case of injection site pain when injection volume is greater than 1 mL, consider splitting the dose into 2 injections.

8.5 Adverse Events

Most AEs observed in the Phase 1-2 clinical trial are common in the AML/MDS population. Common AEs, regardless of relationship to guadecitabine, observed in the AML/MDS populations (relapsed/refractory [r/r] AML, TN AML, TN MDS, r/r MDS, N=308 [Phase 2 Dose Expansion]) treated with guadecitabine (60-90 mg/m² 5-day regimen or 60 mg/m² 10-day regimen in AML only) included injection site AEs, febrile neutropenia, thrombocytopenia, diarrhea, fatigue, nausea, anemia, and constipation. The most common SAEs were febrile neutropenia, pneumonia, and sepsis.

MDS and AML subjects commonly have severely compromised bone marrow and blood counts. Severe or prolonged myelosuppression have been reported as related to guadecitabine, particularly at high doses when the drug may exert cytotoxic effects.

Common AEs, regardless of relationship to guadecitabine, observed in subjects with advanced HCC who failed prior treatment with sorafenib (Study SGI-110-03) who were treated with guadecitabine (45-60 mg/m² 5-day) included neutropenia, injection site events, fatigue, thrombocytopenia, and leukopenia. The most common SAE in these subjects was febrile neutropenia.

Common AEs, regardless of relationship to guadecitabine, observed in subjects with platinum-resistant recurrent ovarian cancer (Study SGI-110-02) who were treated with guadecitabine in combination with carboplatin included neutropenia, nausea, fatigue, vomiting, injection site events, constipation, abdominal pain, diarrhea, leukopenia, anemia, thrombocytopenia, and hypomagnesaemia. The most common SAEs in subjects in these subjects were small intestinal obstruction, vomiting, abdominal pain, febrile neutropenia, neutropenia, and nausea. Three subjects had drug-related SAEs (sepsis, pleural effusion, and febrile neutropenia) with an outcome of death.

9.0 STUDY ASSESSMENTS AND PROCEDURES

9.1 Efficacy Assessments

There are no efficacy assessments in this study, except for survival status which will be documented at the time of withdrawal from the study.

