4.0 INVESTIGATIONAL PLAN

4.1 Overall Study Design

This is a multicenter, open-label extension study for subjects who participated in a previous Astex-sponsored guadecitabine clinical study (including but not limited to SGI-110-01, SGI-110-04, SGI-110-05, SGI-110-06, and SGI-110-07).

Subjects who were still receiving treatment with guadecitabine and in the opinion of the investigator were still benefitting from treatment at the time of database close of the original study will be eligible to participate in this extension study. Approximately 250 subjects could be enrolled at approximately 150 centers in approximately 20 countries worldwide.

Subjects will attend clinic visits on Days 1-5 of each 28-day cycle to receive treatment with guadecitabine. Subjects will receive the same guadecitabine dose and regimen that they were receiving in the last cycle of the prior study. Dose adjustment is permitted under the same guidelines provided in the prior study protocol. Data collection will be limited to treatment exposure, adverse events, concomitant medications, limited laboratory parameters, and survival

status. Other clinical assessments may be performed as part of standard of care but the performance and results of these assessments will not be collected for this study.

Treatment may continue as long as the subject continues to benefit based on investigator judgment. Subjects who need to receive other anticancer therapies or other investigational treatments will be discontinued from this study. Subjects who are withdrawn from treatment will have a safety follow-up visit at 30 ± 7 days after the last guadecitabine dose or prior to beginning alternative anticancer therapy, whichever comes first, and then will be withdrawn from the study.

The primary endpoint is safety as measured by adverse events. Survival status is a secondary endpoint.

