4.2 Discussion of Study Design

This study is designed to allow ongoing treatment with guadecitabine to subjects who have benefitted from guadecitabine treatment in prior Astex-sponsored studies. To minimize the burden on study centers and subjects, assessments have been limited to those required to assess long-term safety.

The sample size of approximately 250 subjects is an estimate. Most of the subjects enrolled in this study will have participated in 1 of 3 ongoing Phase 3 studies that are to enroll a total of approximately 1600 subjects (Studies SGI-110-04, SGI-110-06, and SGI-110-07). Based on the number of death events needed for the primary analysis for each of those studies, the number of guadecitabine subjects receiving treatment at the end of the studies could range from 180 (assuming no treatment difference and no withdrawals) to 326 (assuming all survivors were guadecitabine subjects and no withdrawals). As more guadecitabine clinical studies are conducted, the number of subjects enrolled in this extension study could increase.

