11.9 Procedures for Handling Missing, Unused, and Spurious Data

No imputation of values for missing data will be performed. Data from subjects lost to follow-up will be included in statistical analyses to the point of their last evaluation.

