# 5.2 **Participant Dispositions**

The number and percentage (n, %) of subjects screened, enrolled (by prior study), treated, treatment discontinuation (with reason) and withdrawn from study (with reason) will be summarized. All screened subjects will be included in the disposition analysis.

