### 5.4 Secondary Endpoint Analysis

# 5.4.1 Key/Confirmatory Secondary Endpoint

Long-term overall survival is a secondary endpoint. Survival duration for each subject starting from the time of randomization in the prior study will be determined.

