### 5.4.1.1 **Definition of Endpoint(s)**

Overall Survival (OS)

Overall survival is defined as time, in days, from the time of randomization in the prior study to the date of death (regardless of cause). Subjects without a documented death date at the time of analysis will be censored at the last date known alive.

Survival time in days = (earliest of date of death or censoring – randomization date in the prior study)

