### 5.4.1.2 Main Analytical Approach

The OS curves will be estimated using the Kaplan-Meier method (Kaplan et al 1958). The median (and quartiles) duration of OS and the associated 95% CI (based on the log-log transformation for the survival function) will also be generated.

In addition, OS curves will also be estimated using the Kaplan-Meier method by the disease types (treatment-naive AML, relapse/refractory AML, and relapse/refractory intermediate- or high-risk MDS (including CMML). The median (and quartiles) duration of OS and the associated 95% CI (based on the log-log transformation for the survival function) will be generated for each group of the disease types.

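### Survival status is scheduled only at withdrawal, about 30 days after the last dose, so the SAP's Kaplan-Meier long-term overall survival rests on a censoring assumption that nothing in the plan checks

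*Protocol*

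**What the plan says.** **Objective and endpoint.** Protocol 3.2 asks for long-term survival information. Protocol 4.3.2 names the endpoint only as survival status, and Protocol 11.6 says that survival duration may be determined. The SAP goes further. Section 5.4.1 states: "Long-term overall survival is a secondary endpoint".

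**Data collection.** Protocol 9.1 rules out efficacy assessments except for "survival status which will be documented at the time of withdrawal from the study". The synopsis agrees, and Table 1 has a single survival entry, in the discontinuation/safety follow-up column. Under Protocol 4.1 that visit falls 30 ± 7 days after the last dose, or before alternative anticancer therapy if that comes first, and the subject is then withdrawn. After the 30-day period, Protocol 10.3 requires deaths to be reported only if considered related to treatment or procedures. Protocol 4.2 gives the reason for the light schedule: "assessments have been limited to those required to assess long-term safety".

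**Leaving treatment.** Protocol 4.1: "Treatment may continue as long as the subject continues to benefit based on investigator judgment". The reasons for stopping in Protocol 5.4.1 include unacceptable toxicity and progression needing other therapy, but also noncompliance and the subject's best interest.

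**Analysis.** SAP 5.4.1.1 counts death from any cause, starts the clock at randomization in the prior study, and adds: "Subjects without a documented death date at the time of analysis will be censored at the last date known alive". SAP 5.4.1.2 uses Kaplan-Meier, overall and by disease type, and reports "The median (and quartiles) duration of OS and the associated 95% CI". SAP 5.2 promises that "treatment discontinuation (with reason) and withdrawn from study (with reason) will be summarized", without linking the reasons to survival. Protocol 11.9: "No imputation of values for missing data will be performed". SAP 6.2 records two changes to the planned analyses: the start date and the disease-type analysis.

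**The concern.** Kaplan-Meier treats a censored subject as having the same later risk of death as subjects still under observation at that time. Here, censoring largely follows from stopping treatment. Subjects stay while the investigator sees benefit, and two of the listed reasons for stopping, progression and toxicity, bear on prognosis. A subject who stops in order to start another therapy has the visit beforehand and may contribute almost no follow-up after treatment. The assumption is therefore open to real doubt, and neither document states, checks or varies it.

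What is at stake is how a descriptive result will be read. A median headed long-term overall survival will be taken as survival including the time after treatment. The scheduled data mainly describe survival on treatment plus about a month.

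**Working it through.** The documents give no survival, discontinuation or death rate, so there is no planned figure to reproduce. The textual check is the comparison above: one scheduled survival assessment against an all-cause, long-term Kaplan-Meier estimate. The calculation below only illustrates how the estimate behaves.

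**Assumed inputs (none from the documents).**
- Monthly discontinuation rate d = 0.03 or 0.06.
- Monthly death hazard on treatment h = 0.01, 0.02 or 0.03.
- Death hazard after leaving = k × h.
- Observation ends 1 month after discontinuation, approximating the 30-day visit. Earlier exit for other therapy is not modelled.

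**Formulas, with t in months from extension entry.**
- On treatment: A(t) = exp(-(d+h)t).
- Complete survival: S(t) = A(t) + ∫₀ᵗ d·exp(-(d+h)u)·exp(-kh(t-u)) du.
- Off treatment but still observed: B(t) = the same integrand over the last month, from max(t-1, 0) to t.
- Planned Kaplan-Meier: exp(-∫ h(A + kB)/(A + B) dt).

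**Step 1: is the estimate sensitive to deaths after leaving?** Take d = 0.03, h = 0.02, k = 2 at 24 months. Then S = e^(-1.2) + 0.03 × (e^(-0.96) - e^(-1.2))/(0.05 - 0.04) = 0.301 + 3 × (0.383 - 0.301), about 0.55. The planned estimate is 0.61. For the same d and h:

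| k | 0.5 | 1 | 2 | 3 | 5 |
|---|---|---|---|---|---|
| Complete survival, % | 67 | 62 | 55 | 49 | 43 |
| Planned Kaplan-Meier, % | 62 | 62 | 61 | 60 | 59 |

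Complete survival moves by 24 points and the planned estimate by 3. There is no error at k = 1. This clock (from extension entry) is not the SAP's, so the errors in this table are not the ones to quote.

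**Step 2: the SAP's clock.** Time now runs from randomization, with extension entry assumed uniform between 6 and 36 months later. Before entry a subject is at risk with zero hazard, because entry requires being alive. The terms h(A + kB) and (A + B) are averaged over entry times before the ratio is taken. Complete 36-month survival is the average of S(36 - entry time). Error = planned minus complete. Even at k = 1 an error of 0.8 to 3.6 points appears. It comes from the clock and is a separate matter, so it is subtracted. The rate pairs giving the smallest and largest net errors at k = 0.5 and k = 2 are (percent or points; differences taken before rounding):

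| d, h | k | Complete | Planned | Error | Error at k = 1 | Net |
|---|---|---|---|---|---|---|
| 0.03, 0.01 | 0.5 | 87.9 | 87.4 | -0.5 | 0.8 | -1.4 |
| 0.06, 0.03 | 0.5 | 71.3 | 70.2 | -1.1 | 3.6 | -4.7 |
| 0.03, 0.01 | 2 | 83.7 | 86.9 | 3.2 | 0.8 | 2.4 |
| 0.06, 0.03 | 2 | 58.2 | 68.2 | 10.0 | 3.6 | 6.4 |

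Over all six rate pairs the net error is about -1 to -5 points at k = 0.5, +2 to +6 at k = 2, +4 to +10 at k = 3 and +8 to +15 at k = 5.

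**Step 3: the opposite pull.** SAP 5.4.1.1 counts any documented death. Suppose sites happen to learn of 10% or 25% of deaths after withdrawal, while survivors stay censored near the visit. With k = 1, on the Step 1 clock at 24 months, the error is then -1 to -2 or -2 to -4 points.

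**The case against.** The strongest reply is that this is an openly stated design choice. The study mainly provides continued access to treatment, data collection is deliberately light, and SAP 2.0 and 5.1 make every analysis descriptive. Long-term is also not an empty label: the clock starts at prior-study randomization, and Protocol 2.1 describes eight subjects treated for 2.8 to 5.6 years. All of this stands, and it limits the consequence to interpretation.

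Follow-up is also not strictly closed at day 30. Protocol 9.3.4 asks for at least 30 (+7) days, or until related events resolve or stabilise. Protocol 5.4.2 asks for follow-up information on subjects withdrawn prematurely. The SAP's last date known alive is not capped at the visit. These provisions can yield some later dates. But the two protocol sections are directed at safety, and none of the three schedules a survival contact after withdrawal. It is likewise an inference, though a plausible one, that later deaths become known more readily than continued survival.

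Table, listing and figure specifications sit in a separate document (SAP 1.0), so a listing of censoring dates there cannot be excluded. A sensitivity analysis, however, belongs in the SAP.

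Finally, the rates and k are assumed. A reader might infer that the reported survival will be overstated by a known amount. The documents do not support that: the sign depends on k, and incidental late deaths pull the other way.

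**Conclusion.** The point holds as a gap between label and data. No survival follow-up is scheduled after withdrawal, censoring is plausibly informative, and the plan contains no check. Over the assumed grid, the planned estimate hardly responds to mortality after leaving.

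Overstatement is the more plausible direction, because progression and toxicity are listed reasons for stopping. Neither direction nor size can be determined from the documents. The 36-month figures on the SAP clock, about -1 to -5 points if the hazard halves and +2 to +6 if it doubles, are net of the clock effect. They rest on constant hazards, the assumed rates and an assumed 6 to 36 month entry.

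It would go too far to infer that the analysis is invalid or must be dropped. It is descriptive, no hypothesis or error rate depends on it, and it remains usable if its follow-up limit is stated. It is worth correcting before the results are reported.

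**What to change.** Revise SAP 5.4.1 and record the change in SAP 6.2:

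1. **Label.** Keep the analysis in SAP 5.4.1.1, but state that follow-up ends about 30 days after the last dose or at other anticancer therapy. Do not present the median as long-term overall survival without that limit.
2. **Supportive analysis.** Add a Kaplan-Meier analysis that counts deaths only within that window and censors at its end, so that deaths and survival are ascertained alike. List later documented deaths separately. This removes the uneven ascertainment, not the informative censoring.
3. **Sensitivity analysis.** On the SAP clock, vary the death hazard after leaving relative to that on treatment, below and above 1 (for example 0.5, 1, 2, 3, 5). Compare each result with the one at ratio 1, so that the clock effect is not mistaken for censoring bias. Describe it as driven by assumption. If death times are imputed, state this as an exception to Protocol 11.9.
4. **Censoring description.** Report reasons for censoring and time from last dose to censoring, building on SAP 5.2.

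The cost is a SAP revision, a few outputs and a more qualified survival figure. No new data are needed. These steps show the limit; they do not supply the missing follow-up.

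Two additions are optional. One is the cumulative incidence of death on study (Aalen-Johansen) from the first SGI-110-12 dose, which answers a different question on a different clock. The other is a vital-status check at study close, where consent allows. It would serve the objective better, but it needs an amendment with IRB/IEC approval (Protocol 14.4) across about 150 planned centers, when the SAP already describes end-of-study analyses.
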